Visit 1: After enrollment, the participant will receive EDM (Electronic Data Monitoring) caps for up to six scheduled medications that they are receiving. A manual pill count will be completed for this visit either in clinic or via telephone. If the participant has their medications with them at Visit 1, the manual pill count will be completed by the study team pharmacist, pharmacy student, or a member of the research team in clinic. The study staff completing manual pill counts will complete hazardous drug safe handling training prior to contact with patient medication. If the participant does not have their medications with them at Visit 1, the study team will arrange a time to call the participant to complete the manual pill count over the telephone.

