Visit 2: After completion of week 4, participants will have an outpatient study visit for: 1) EDM cap data download and manual pill count. The study staff will either call, text, or email the participant prior to Visit 2 to remind them to bring their medications and eCAPs to Visit 2 for EDM cap data download and manual pill count. A manual pill count will be completed for this visit either in clinic or via telephone. If the participant has their medications with them at Visit 2, the manual pill count will be completed by the study team pharmacist, pharmacy student, or a member of the research team in clinic. The study staff completing manual pill counts will complete hazardous drug safe handling training prior to contact with patient medication. If the participant does not have their medications with them at Visit 2, the study team will arrange a time to call the participant to complete the manual pill count over the telephone. Participants, however, will be encouraged to bring their pill bottles with them to this visit. 2) To download Dosecast program and receive instruction in smartphone medication reminder application use by the CRA. Each participant will be given an individual passcode that will allow Montuno Software to identify app usage and to share data with the study team. Participants will not enter any personally identifiable information into the app, and no PHI will be shared with Montuno Software. 3) If a participant does not attend the in-person Visit 2 (Week 4), there will be an option to mail, email, or send via RedCAP the questionnaire that would have been completed at that visit. If the participant does not attend the in-person Visit 2 (Week 4), the initiation of the Weeks 5-12 questionnaires will be deferred until the participant has downloaded the Dosecast app, set up the reminders, and received instruction on its use.

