Visit 3: After completion of week 12, participants will have a final study visit in an outpatient setting for EDM cap data download and manual pill count. The study staff will either call, text, or email the participant prior to Visit 3 to remind them to bring their medications and eCAPs to Visit 2 for EDM cap data download and manual pill count. A manual pill count will be completed for this visit either in clinic or via telephone. If the participant has their medications with them at Visit 3, the manual pill count will be completed by the study team pharmacist, pharmacy student, or a member of the research team in clinic. The study staff completing manual pill counts will complete hazardous drug safe handling training prior to contact with patient medication. If the participant does not have their medications with them at Visit 3, the study team will arrange a time to call the participant to complete the manual pill count over the telephone. Participants, however, will be encouraged to bring their pill bottles with them to this visit. If a participant does not attend the in-person Visit 3 (Week 12), there will be an option to mail, email, or send via RedCAP the questionnaire that would have been completed at that visit.

Estimated time to complete questionnaires can be found in the Measures Timetable (uploaded to the application).

Phone calls, emails, and/or text messages will be used to follow-up about other study procedures as needed.

Dosecast Application use:

Montuno Software will be issuing to study staff a pool of unique, randomly-generated patient credentials, each of which will be distributed to a study participant. The study participant will be instructed to download and install the free Dosecast

app from the Apple or Google app store and enter the provided credentials upon first use. As participants use the app, their adherence data will be silently collected by the app and securely and automatically uploaded to Montuno's cloud servers. Data will be downloaded by the CRA from Montuno's cloud servers regarding amount and nature of use of smartphone application by participants.

Data storage and analysis:

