Change in adherence behavior will be assessed pre-intervention (end of week 4) and post-intervention (end of week 12) based on (1) one self-reported multiple-choice question and 8 questions in the Morisky Medication Adherence Scale (MMAS-8); (2) EDM cap count; and (3) manual pill count. Pre-intervention and post-intervention self-reported adherence behavior will be compared, and the proportion of participants reporting higher adherence post-intervention, as well as associated 95% confidence intervals, will be calculated overall and by intensity of medication regimen. Rates of medication adherence pre-intervention (weeks 1 through 4) and post-intervention (weeks 5 through 12) will be calculated based on EDM cap count and manual pill count separately by dividing observed pill count by expected pill count. Expected pill count will be determined based on the participant's prescribed oral medication regimen. Paired differences in adherence rates (post-intervention minus pre-intervention) based on EDM and manual counts, respectively, will be generated for each participant, and mean change and associated 95% confidence intervals will be calculated. To evaluate the association between self-reported adherence behavior and adherence behavior measured by EDM caps and manual pill counts, EDM caps and manual pill count estimates will be reoperationalized as ordinal levels corresponding to the ordinal levels used in the self-report measure of adherence behavior. Cohen's kappa, an estimate of rating agreement, will then be calculated. We will summarize participants' perspectives on feasibility and acceptability using the feasibility and acceptability questionnaire.

Overall indices of all potential predictors of adherence (i.e., allocation of treatment responsibility, attitudes towards medications, perceived behavioral control for adherence, subjective norms, intention to adhere, past adherence behavior, self-efficacy, cognitive representation of medicine, barriers to adherence, psychological symptoms, demographic factors) will be calculated. We will summarize mean levels of these potential predictors at all timepoints available and will calculate mean change in these predictors over time. We will use regression-based analyses to examine the potential impact of these predictors prior to use of the SmartPhone app on adherence. We will also explore associations between

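### Manual pill counts are planned at three visits with no stated record of pills dispensed in between, so the manual adherence rate is wrong or underivable for any medicine refilled in the interval

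*Combined protocol and SAP*

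**What the plan says.** All references are to section 4, Study Information, of the combined protocol and SAP.

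Item 6 (Study visits) describes three manual counts. Visit 1: "A manual pill count will be completed for this visit either in clinic or via telephone". Visit 2: "After completion of week 4, participants will have an outpatient study visit for: 1) EDM cap data download and manual pill count". Visit 3, after week 12: "participants will have a final study visit in an outpatient setting for EDM cap data download and manual pill count". A telephone count is allowed at each visit if the medicines are not brought.

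Item 9 sets the analysis: "Rates of medication adherence pre-intervention (weeks 1 through 4) and post-intervention (weeks 5 through 12) will be calculated" from the EDM caps and the manual counts separately, by "dividing observed pill count by expected pill count". For the denominator, "Expected pill count will be determined based on the participant's prescribed oral medication regimen". The endpoint follows: "Paired differences in adherence rates (post-intervention minus pre-intervention) based on EDM and manual counts, respectively, will be generated for each participant". The manual rate is also cut into ordinal levels for a kappa against self-report and is a dependent variable in a GEE model.

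No text on visits, questionnaires, app data, data storage or analysis mentions refills, dispensed quantities, dispensing dates, pharmacy records or second bottles.

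**The concern.** Two pill counts give pills taken only if nothing was added to the bottle between them. The prescribed regimen supplies how many pills should have been taken. It does not say how many were dispensed. Once a bottle is refilled, the difference between two counts no longer measures consumption, and an analyst with only the planned data cannot repair it.

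The manual count is one of three named sources for change in adherence. A negative rate has no sensible place among the ordinal levels needed for kappa. A rate that cannot be derived because of an unknown refill also has no handling rule: the missing-data text in item 9 anticipates only non-compliance, withdrawal and inpatient care.

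**Working it through.** **The plan's own figures.** The plan gives no precision figure for the manual rate. Its only design figure is the 95% interval width for eligibility, enrollment and retention rates with 25 participants (20% to 40%). Exact binomial intervals reproduce it: 20.3 points at 1/25 and 40.9 points at 50%. The present point does not depend on it.

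**Inputs from the plan.** Counts at Visit 1, after week 4 and after week 12, so the intervals are 28 and 56 days. At least 25 participants. Up to six capped medicines each.

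**Assumptions, since the plan gives no figures.** One pill a day; a fill of L pills every L days; fill date random relative to Visit 1; true adherence 90% in both periods; one medicine per participant.

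**Formulas.**
- Pills taken = start count + dispensed - end count.
- Rate without dispensing data = (start count - end count) / T = 0.90 - (refills × L) / T, with T = 28 or 56.
- Expected refills = T / L.
- Chance of at least one refill = min(1, T / L).

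**Size of one error.** One unrecorded 30-pill refill in weeks 1-4 gives 0.90 - 30/28 = -17%. Two in weeks 5-12 give 0.90 - 60/56 = -17%.

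**Range over fill intervals.** The SD is that of the post-minus-pre difference from refills alone, by simulation. The half-width is 2.064 × SD / √25, using the t quantile on 24 degrees of freedom.

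| L (days) | Expected refills, weeks 1-4 / 5-12 | Chance of at least one, weeks 1-4 / 5-12 | SD of difference | 95% half-width, 25 participants |
|---|---|---|---|---|
| 14 | 2.0 / 4.0 | 100% / 100% | 0 | 0 |
| 28 | 1.0 / 2.0 | 100% / 100% | 0 | 0 |
| 30 | 0.93 / 1.87 | 93% / 100% | 0.34 | 14 points |
| 60 | 0.47 / 0.93 | 47% / 93% | 1.17 | 48 points |
| 90 | 0.31 / 0.62 | 31% / 62% | 2.20 | 91 points |

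The mean rate without dispensing data is about -10% in both periods on every row, so the mean difference is about 0. At 14 or 28 days the same amount is subtracted from both rates. The difference then survives, although each rate is impossible.

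**Participants untouched by refills.** The chance of no refill over the full 84 days is 1 - 84/L: zero for L of 60 or less, and about 7% at L = 90. With three independently filled medicines at L = 90, the chance that none is refilled is (1 - 28/90)³ = 33% in weeks 1-4 and (1 - 56/90)³ = 5% in weeks 5-12.

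**Direction, checked exactly.** Take 30-pill fills, one pill a day, perfect adherence and a refill when empty, and try every Visit 1 count from 0 to 29.
- Counts 0 to 23: one refill, then two. Both rates are 1 - 30/28 = 1 - 60/56 = -7%. Spurious change 0 (24 counts).
- Counts 24 to 27: one refill, then one. The rates are -7% and 1 - 30/56 = 46%. Spurious change +54 points (4 counts).
- Counts 28 and 29: no refill, then two. The rates are 100% and -7%. Spurious change -107 points (2 counts).

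The mean is (4 × 53.6 - 2 × 107.1) / 30 = 0. The SD is √[(4 × 0.536² + 2 × 1.071²) / 30] = 0.34, which agrees with the table.

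**The case against.** **The defect may be only an omission from a summary.** The document is an IRB application. The pill-count form and the uploaded Measures Timetable are not part of it, a study pharmacist may do the counts, and setting the expected count requires knowing the regimen. A refill field may exist on a form. This stands as a limit: the safe statement is that items 6 and 9 do not state such a step. Even so, item 9 has no term for dispensed pills, so a recorded refill would not enter the rate as written.

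**The observed count could be read differently.** If it means pills remaining, the expected remaining count is start plus dispensed minus prescribed, and the same quantity is missing. The weekly items cover percentage adherent, missed doses and reasons. Dosecast is installed only at Visit 2, so it cannot serve weeks 1-4.

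**Telephone counts do not make the quantity unrecoverable.** A participant counting by telephone has the bottle and can read out its label. The plan also gives no figure for how many counts will be by telephone.

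**A reader might infer bias against the app.** The app period is twice as long and contains twice as many expected refills. The documents do not support the inference, because the denominator doubles too: a missed 30-pill refill costs 107 points over 28 doses but 54 points over 56. The app period is worse in number of refills and, for fill intervals above 28 days, in the share of counts that cannot be derived. It is not worse in mean error, and the baseline rate is the noisier of the two at the 30-, 60- and 90-day intervals. Bias against the app needs bottles that tend to be full near Visit 1, and nothing in item 6 ties Visit 1 to a fill.

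**Impact is bounded.** This is a feasibility pilot, and impossible negative rates would be noticed. That makes lost or noisy data likelier than hidden bias, but does not restore the measure.

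**Conclusion.** The point holds as a missing input and an undefined numerator. As written, the manual rate is valid only for a medicine not refilled between the two counts. Under the assumed once-daily regimen, no participant avoids a refill across both periods if fills come every 60 days or less, and about 7% do at 90 days.

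With random fill dates the consequence is noise and loss. Refills alone would give the mean paired change a 95% half-width of about 14, 48 or 91 points at 30, 60 or 90 days, with 25 complete participants and one medicine each. There is no mean shift. If a 30-day bottle is full at Visit 1 and true adherence is 90%, baseline reads 90% and the app period -17%, a spurious -107 points. That is a special case.

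The defect is confined to the manual-count rate, its paired difference, its kappa and its GEE model. The EDM and self-report measures do not use a pill balance. All sizes rest on assumed fill intervals.

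**What to change.** In item 6, at Visits 1, 2 and 3, add: at each count, in clinic or by telephone, count all bottles in use for every medicine. From Visit 2 on, also record the quantity and date of each supply dispensed since the last count. The source is the bottle label (read out by the participant if by telephone) or the pharmacy record.

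In item 9, define observed pills for the manual rate as start count + dispensed - end count. Set the manual rate to missing for a medicine whose dispensing record is incomplete, and add this as a named reason in the missing-data text. With complete records the assumed 90% is recovered in both periods at any fill interval.

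The cost is a few fields on a form completed by staff already doing the count, a slightly longer visit or call, and some manual rates that become missing instead of wrong.

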We will enter in all data, including PHI, into a secure site (i.e., the REDCap system) here at the University of Utah. REDCap features include differentiated user roles and privileges, user authentication and authorization security, electronic signatures, SSL encryption, and comprehensive auditing to record and monitor access and data changes. De-identified data will be downloaded from REDCap onto University of Utah, secure servers and will be accessed using encrypted, password-protected computers.

Montuno Software will extract the adherence data from Dosecast corresponding to all the credentials used by study participants and publish the data on a password-protected FTP site for study administrators to download. Data will be removed from the FTP site 1 week after publishing and the data has been downloaded by the CRA. This data will also be stored on University of Utah, secure servers and will be accessed using encrypted, password-protected computers.

The PI will work with external investigators (see external investigators) who will assist with data analysis. The PI will only share a limited, de-identified dataset with the external investigators. This limited dataset will not include PHI. In order to ensure that PHI has been completely removed from this dataset, the CRA will remove all identifiers from the data and the PI will verify at all identifiers have been removed before data is shared with the external investigators.

7. Are all procedures for research purposes only (non-standard or non-standard of care procedures)?

Yes No

If no, list the procedures that are performed for research purposes only (non-standard or non-standard of care procedures):

8. Is there a safety monitoring plan for this study?

Yes No

9. Provide a summary of the statistical methods, data analysis, or data interpretation planned for this study. Factors for determining the proposed sample size (e.g., power) should be stated.

To explore the feasibility and acceptability of using a smartphone medication reminder application to promote adherence to oral medications and to characterize application use.

We anticipate enrolling at least 25 participants for this pilot study of medication reminder application feasibility and acceptability. Eligibility, enrollment and retention rates will be estimable with 95% confidence intervals ranging in width from 20% (for estimates near 5% or 95%) to 40% (for estimates near 50%).

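### The only statistic named for change in self-reported adherence is the share reporting higher adherence, which omits participants who got worse and has no fixed null value

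*Combined protocol and SAP*

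**What the plan says.** The relevant text is item 9 of the Study Information (statistical methods), in the paragraph on change in adherence behavior.

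- **Self-report instruments:** "one self-reported multiple-choice question and 8 questions in the Morisky Medication Adherence Scale (MMAS-8". Item 6 (Questionnaires) describes the MMAS-8 as seven yes/no items and one 5-point item. It does not give the number of response levels of the multiple-choice item.
- **Self-report analysis:** "Pre-intervention and post-intervention self-reported adherence behavior will be compared", with no contrast, test or model named. The same sentence then names one statistic: "the proportion of participants reporting higher adherence post-intervention, as well as associated 95% confidence intervals, will be calculated", overall and by regimen intensity.
- **Count-based measures, same paragraph:** "Paired differences in adherence rates (post-intervention minus pre-intervention) based on EDM and manual counts, respectively, will be generated for each participant", after which "mean change and associated 95% confidence intervals will be calculated".
- **Size and purpose:** "We anticipate enrolling at least 25 participants for this pilot study of medication reminder application feasibility and acceptability".

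No share lower, share unchanged, self-report mean change or reference value is given. The rest of item 9 does not supply one:

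- The GEE models take cap and pill-count adherence as the outcome.
- The kappa analysis concerns agreement between measures.
- Mean change is planned for predictors, and past adherence behavior is on that list. Item 6 assigns that construct to a separate theory-based questionnaire, not to the multiple-choice item or the MMAS-8.
- The Missing Outcome Data section adds a non-missing denominator, worst-case substitution and summarising over weeks 1-4 and weeks 5-12.

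**The concern.** Change has a direction, and this summary records only one of the two. On a repeated ordinal item some participants move up and some move down through measurement noise alone. The share moving up therefore has to be read against the share moving down, and there is no control arm to supply that reference.

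Neither obvious reference value works. Zero is wrong because noise moves some people up. Fifty percent is wrong because ties are expected. The share also depends on the ceiling: a participant already in the top category cannot report higher. If, say, 10 of 25 started there, the largest possible share would be 15/25 = 60%.

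What is at stake is how one of three planned assessments of adherence change is read, overall and again within each regimen-intensity group.

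**Working it through.** **1. The plan's own precision figure.** The plan gives "95% confidence intervals ranging in width from 20% (for estimates near 5% or 95%) to 40% (for estimates near 50" percent. This is stated for eligibility, enrollment and retention rates, but it is the only precision figure for proportions. With n = 25 and the exact (Clopper-Pearson) method:

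- 1/25 gives 0.1% to 20.4%, width 20.2 points
- 12/25 gives 27.8% to 68.7%, width 40.9 points

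Both match the rounded figures. Wald gives 17.1 points at 5% and 39.2 at 50%; Wilson gives 18.8 (1/25) and 36.5 (12/25). The exact method fits best and is used below.

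**2. Formulas.** Let h, s and l be the numbers higher, same and lower, with h + s + l = n = 25.

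- Planned summary: h/n with its exact 95% CI.
- Signed summary: d = (h - l)/n, with SE = sqrt{[(h + l)/n - d²]/n} and 95% CI d ± 1.96 SE.

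**3. Illustrative splits.** The documents give no rates, so these are assumptions.

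| h / s / l | Planned: share higher (exact CI) | Net share d | SE | 95% CI for d | Exact sign test p |
|---|---|---|---|---|---|
| 8 / 9 / 8 | 32% (14.9% to 53.5%) | 0 | sqrt(0.64/25) = 0.160 | -31 to +31 points | 1.00 |
| 8 / 4 / 13 | 32% (14.9% to 53.5%) | -20 points | sqrt[(0.84 - 0.04)/25] = 0.179 | -55 to +15 points | 0.38 |
| 5 / 15 / 5 | 20% (6.8% to 40.7%) | 0 | sqrt(0.40/25) = 0.126 | -25 to +25 points | 1.00 |
| 5 / 8 / 12 | 20% (6.8% to 40.7%) | -28 points | sqrt[(0.68 - 0.0784)/25] = 0.155 | -58 to +2 points | 0.14 |

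Within each pair the planned output is identical. With h fixed at 8, the net share can be anything from (8 - 0)/25 = +32 points to (8 - 17)/25 = -36 points, and the planned summary does not change. This step needs no modelling assumption.

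**4. How large the share is under no change.** This depends on assumptions: a latent normal cut into 5 levels, with assumed pre/post correlations and assumed top-category shares.

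- *One measurement before and one after, no true change:* 14% to 31% higher (correlation 0.5-0.8, 21-69% in the top category). A second set of cut-points (correlation 0.5-0.7) gave 21% to 33%. With that second set, a true fall of 0.3 SD still left 15% to 24% higher, which overlaps the no-change range.
- *Averaged over 4 weeks before and 8 weeks after, as the Missing Outcome Data section suggests:* about 26% to 46% higher under no change, and about 10% to 23% after a fall of 0.3 SD.

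Under averaging, an observed 30% could be close to the no-change value (26%) or well below it (46%), depending on ceiling and correlation. The null value is not fixed in either setting.

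**The case against.** The strongest reply has five parts.

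- **A comparison is planned.** The text says pre and post self-report will be compared, so a signed contrast is not excluded. This stands: the fault is that none is specified and the only named statistic is one-directional. It is not that the plan rules a signed contrast out.
- **The share need not flatter the app.** A reader might infer that the summary will look positive under no change or even deterioration. The documents do not support that. They set no null of 0, no success threshold and no efficacy claim on this proportion. Read against 50%, the 8/9/8 split would look unfavourable. Nor does the interval exclude 0 whenever anyone improves: that holds for the exact method, but the plan names no method, and a Wald lower limit is below 0 for 1, 2 or 3 of 25.
- **The simulated shares rest on invented inputs.** This stands. The levels, correlation and ceiling are assumed, and a 5-level item does not represent the MMAS-8. The single-measurement version also ignores the planned averaging, under which the share responds more clearly to a fall. It is unclear which applies to self-report, because item 9 also describes assessment at the end of week 4 and the end of week 12. The simulations are illustrations; the conclusion rests on step 3.
- **Two of the three adherence measures are handled properly, in a feasibility pilot.** This stands and limits the consequence. A reader might also take the self-report share to be the study's main result; nothing in the plan gives it that place.
- **The net share would be imprecise.** True: both deterioration examples have intervals that include 0. They still show the direction and the uncertainty, which the planned summary does not.

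**Conclusion.** The concern holds as a gap in the self-report summary. As specified, the named statistic cannot separate stability from deterioration: with 25 participants, 32% (14.9% to 53.5%) is compatible with net changes of 0 and of -20 points, and 20% (6.8% to 40.7%) with 0 and -28 points. This rests only on n = 25, on the definition of the statistic and on the exact interval; the splits are illustrative.

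The effect is on interpretation of one planned assessment. It does not touch the sample size, the feasibility and acceptability aim, or the cap and pill-count analyses. It does not show that the plan is biased in favour of the app. The change is worth making because it is cheap and brings self-report into line with the signed paired change that the same paragraph already uses for counts.

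**What to change.** In item 9, after the sentence on self-report:

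1. Report the numbers and shares higher, unchanged and lower, overall and by regimen intensity.
2. Give a signed paired summary with a 95% CI: the net share (higher minus lower) for the multiple-choice item, and the mean paired change for the MMAS-8 score.
3. State how many participants were in the top category before the app and so could not rise.
4. Say whether self-report is compared at the end of weeks 4 and 12 or as summaries over weeks 1-4 and weeks 5-12, since this affects how many ties to expect.

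An exact sign test or Wilcoxon signed-rank test may be named as the comparison, but in an estimation-oriented pilot it is optional.

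Cost: a few sentences and slightly more reporting, with no new data. The net share will be lower than the share higher whenever anyone gets worse, so the reported figure will look less favourable.

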changes in these predictors and changes in adherence. For example, we will explore whether increased self-efficacy is associated with improved medication adherence.

We will further conduct a series of analyses to examine the relationship between potential predictors of adherence and intervention outcomes. Models will be adjusted for within-subject correlation associated with repeated measurement.

Association of potential predictors of adherence with adherence to oral medications. We will fit a GEE model with potential predictors as the independent variable perceived behavioral control and dependent variable adherence behavior (from EDM caps and manual pill counts, respectively), adjusted for pre-/post-intervention, accounting for within subject correlation.

Sensitivity analyses will be conducted to assess the robustness of analytic conclusions when pre-intervention and post-intervention measures are analyzed separately; and accounting for intensity of medication regimen.

Missing Outcome Data:

We anticipate three mechanisms by which data may be missing in this study: non-compliance, withdrawal and inpatient care. Missing data will be summarized descriptively. Potential associations of missingness due to non-adherence or withdrawal with demographic factors and prior medication reminder application usage will be explored. For this study, participants who withdraw prior to beginning the intervention will be excluded from analyses of the Secondary Aims. We will reduce the analytic impact of missing data by pre-summarizing outcome measures across the pre-intervention interval (weeks 1 through 4) and separately across the post-intervention interval (weeks 5 through 12). For calculation of means and proportions, only non-missing observations will be included in the denominator. In addition, we will perform a series of sensitivity analyses in which we will substitute the worst-case outcome for those observations that are missing due to non-adherence or withdrawal.

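### The adherence rate is observed over expected count with no ceiling and no rule for combining medicines, so openings that are not doses can offset missed doses

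*Combined protocol and SAP*

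**What the plan says.** Item 9 of the combined protocol and SAP obtains adherence rates for weeks 1–4 and weeks 5–12 from "EDM cap count and manual pill count separately by dividing observed pill count by expected pill count". On the denominator it says: "Expected pill count will be determined based on the participant's prescribed oral medication regimen". Under Visit 1 in item 6, each participant receives "caps for up to six scheduled medications that they are receiving". The missing-data paragraphs of item 9 confirm that outcomes are summarised once over each whole interval.

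The rates are then used in three places:

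- the main change estimate, described as "Paired differences in adherence rates (post-intervention minus pre-intervention) based on EDM and manual counts", with a mean and 95% confidence interval;
- the GEE model, whose outcome is adherence from caps and from manual counts in turn, with no other definition given;
- the agreement analysis, where the cap and count estimates are "reoperationalized as ordinal levels corresponding to the ordinal levels used in the self-report measure of adherence behavior" before kappa is calculated.

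The plan does not state a maximum for the rate, what happens to surplus openings, how an opening becomes a pill count, what observed means for a manual count, or how several medicines become one rate.

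**The concern.** A cap records that a bottle was opened, not that a dose was taken. Under an interval ratio with no ceiling, an opening to check, refill or count pills is worth as much as a dose. It can raise a rate above 100%, or fill the gap left by a dose missed on another day. The first can show improvement where none is possible; the second hides non-adherence.

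The protocol itself gives occasions for such openings: a manual pill count is scheduled at each of Visits 1, 2 and 3, and counting normally means opening the bottle. No control group is described that would cancel an artefact specific to one period. The sensitivity analyses in item 9 cover separate pre and post analyses, regimen intensity, and worst-case substitution for missing data; none deals with over-counts. The paired change and the GEE outcome therefore inherit the problem directly.

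**Working it through.** **The plan's own figure.** Item 9 gives no figure for adherence. Its only precision statement is for eligibility, enrollment and retention rates: interval widths of 20% to 40% with 25 participants. This reproduces with exact 95% intervals: 1/25 gives 0.1% to 20.4% (width 20.3%) and 12/25 gives 27.8% to 68.7% (width 40.9%). The present point does not depend on it.

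**Inputs from the documents.** Weeks 1–4 = 28 days; weeks 5–12 = 56 days; up to six medicines; at least 25 participants; pill counts at Visits 1, 2 and 3. All surplus rates below are assumptions, because the documents give none.

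**1. Offset within one medicine.** Rate = observed / expected. Once-daily medicine over 56 days, doses taken on 42 days, 14 extra openings:

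- as written: (42 + 14)/56 = 100%;
- at most one opening counted per day: 42/56 = 75%.

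**2. Openings at the study's pill counts.** Assume a once-daily medicine and one recorded opening per count. Each adds 1/28 = 3.6 points to the first interval or 1/56 = 1.8 points to the second. Visits 2 and 3 follow completion of weeks 4 and 12, so the interval each opening falls in, if any, depends on where the intervals are cut. The false change (post minus pre) is:

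- Visit 2 in the first interval, Visit 3 in the second: 1/56 − 1/28 = −1.8 points;
- Visits 1 and 2 in the first, Visit 3 in the second: 1/56 − 2/28 = −5.4 points;
- Visit 1 in the first, Visits 2 and 3 in the second: 2/56 − 1/28 = 0;
- only Visits 2 and 3 recorded, both in the second: 2/56 = +3.6 points.

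**3. Offset between medicines, only if counts are pooled or uncapped ratios averaged.** With equal expected counts:

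- two medicines at 125% and 75%: (1.25 + 0.75)/2 = 100%, against (1.00 + 0.75)/2 = 87.5% with each capped first;
- five medicines at 120% and one never taken: 5 × 1.20/6 = 100%, against 5/6 = 83.3%; with the five at 110%, 5 × 1.10/6 = 91.7%, against 83.3%.

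**4. Effect on the mean change.** Simulation under assumed conditions: 25 participants, one once-daily medicine, true adherence drawn from Beta(8,2) (mean 0.8) and unchanged between intervals, extra openings only in weeks 5–12 and only on days already dosed, 4,000 runs. The expected false change is 0.8 × the extra-opening rate.

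| Dosed days with an extra opening | Uncapped: mean change | Uncapped: 95% CI wholly above zero | Interval total capped: mean change | Daily cap: mean change |
|---|---|---|---|---|
| 5% | +4.0 points | 54% of runs | +3.7 | about 0 |
| 10% | +8.1 points | 97% | +6.9 | about 0 |
| 20% | +16.0 points | 100% | +11.5 | about 0 |

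Under the daily cap the interval lay wholly above zero in 2.1% to 2.6% of runs. That column is near zero by construction, because the extra openings were placed on dosed days. Putting the same surplus in weeks 1–4 reverses the sign: 0.8 × 5% gives −4.0 points. The table shows sensitivity, not a forecast. It also shows that capping only the interval total removes little of the distortion.

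**The case against.** Item 9 answers a request for a summary of methods, and silence is not a rule. A reader might infer that the plan pools counts over six medicines, keeps values above 100%, treats pills missing from a bottle as taken, and so biases the result in favour of the app. The documents support none of these steps. No combination rule is given; retention of values above 100% is not stated; observed is undefined for manual counts, so reading it as pills gone from the bottle is natural but remains a reading; and the bias could run either way. These limits stand.

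A strict calendar-day cap also has a fault of its own. Suppose all 28 doses of a once-daily medicine are taken in weeks 1–4, three of them after midnight. The interval ratio is 28/28 = 100%, but the daily-capped rate is 25/28 = 89.3%. If reminders then removed late dosing, the capped rate would show 100 − 89.3 = +10.7 points with no dose ever missed. This stands, and the fix must allow for it. Nor can manual counts be resolved by day, and the documents do not say that cap records are time-stamped.

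The stakes are also limited: this is a feasibility pilot, change is estimated with no stated decision rule, and caps, manual counts and self-report are reported separately, so a distortion in one may be noticed. Kappa may be less exposed if the top ordinal level absorbs values above 100%, though offset below 100% remains.

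What the objection does not remove is offset over time within a medicine. That follows directly from an interval ratio with no ceiling and needs no assumption about pooling. It does assume that openings are counted unscreened, and the plan mentions no screening.

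**Conclusion.** The point holds in limited form. For cap data, the stated ratio lets openings that are not doses score as adherence and offset missed doses within a medicine over an interval, and no planned analysis would reveal it. Offset between medicines is conditional on an aggregation rule that the plan does not give. For manual counts, the point depends on what observed means.

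The size and direction of bias in the pre/post change are unknown. For scale, one stray opening of a once-daily medicine is worth 3.6 points in weeks 1–4 and 1.8 in weeks 5–12, and the visit-count scenarios span −5.4 to +3.6 points. A finding that the adherence change is biased towards benefit would go beyond the documents. The feasibility and acceptability results do not use this ratio. The paired change and the GEE do, so the rule should be settled before those analyses are run.

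**What to change.** Add to item 9:

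1. Exclude cap openings made at scheduled pill counts where they can be identified.
2. Where cap records are time-stamped, count openings per medicine up to the number prescribed per dosing day, with a day boundary or grace window that keeps late-night doses with the intended day.
3. Where they are not, and for manual counts, cap each medicine's interval count at its expected count, and acknowledge that this does not remove offset below 100%. Define observed for both sources.
4. Sum capped counts over medicines and divide by the summed expected count.
5. Use this rate for the paired change, the GEE and the agreement analysis; report the share of values above expected; and give the uncapped ratio as a sensitivity analysis.

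The cost is a few lines of programming and no new data collection, provided the cap downloads hold times; if they do not, step 3 is the fallback. The downside is that capping is one-sided. It trims over-counts but leaves under-counts, such as several doses removed at one opening, and may miss some off-schedule doses. The uncapped analysis helps to show how much this matters.
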